4. PARTICIPANT IDENTIFICATION AND RECRUITMENT

4.1. Study Participants

68 people who have had a stroke and want to improve their sleep.

4.2. Inclusion Criteria

- Participant is willing and able to give informed consent for participation in the study.
- Male or Female, aged 18+ years
- > 3 months post stroke
- Interest in improving sleep
- Can understand verbal and written English well enough to engage with the programme and study procedures (with assistance from carer if needed).
- Current stable health
- Reliable access to internet
- Currently living in the U.K

4.3. Exclusion Criteria

The participant may not enter the study if ANY of the following apply:

- Serious physical health concerns necessitating surgery, scheduled in the next 5 months
- Undergoing a psychological treatment programme for insomnia (with a health professional or online)
- Pregnancy
- Uncontrolled seizures
- Untreated diagnosed obstructive sleep apnoea
- Habitual night shift, evening or rotating shift-workers
- Other serious clinical condition that may affect participation in the study

5. STUDY PROCEDURES

5.1. Recruitment

Participants will be identified through several channels, including advertising online via social media e.g. Twitter and Facebook, newspaper advertisements, relevant charity websites and by presentations at local stroke support groups and giving out leaflets (attached) at our public engagement events.

Additionally, we will re-contact participants from previous studies who have consented to being contacted about future research studies by email.

5.2. Screening and Eligibility Assessment

We will identify participant eligibility from discussion with any interested people via email or phone conversations. Through these channels we will ascertain whether participants have had a stroke and meet the inclusion criteria. If they meet these criteria and are interested in the study, we will send them a copy of the participant information sheet (PIS) and the consent form.

5.3. Informed Consent

Written versions of the Participant Information and Informed Consent will be sent to the participants. The participant will be allowed as much time as they wish to consider the information, and have the

opportunity to question the investigators, their GP or other independent parties to decide whether they will participate in the study. Written Informed Consent will then be obtained by means of participant dated signature.

5.4. Randomisation

Participants will be randomised into the CBT-I or control group based using an online randomisation software (rando.la) with minimisation of between group differences based on baseline SCI score and age.

All participants randomised to the control group will be offered the opportunity to undergo the Sleepio programme after completion of the 8-week follow up.

5.5. Baseline Assessments

After the signed consent form has been received by the researchers, the participant will be sent the GAD-7, PHQ-9, SCI, Stroke Impact Scale-8, Stroke Efficacy questionnaire and EQ-5D-5L to complete. Participants will also receive a questionnaire asking them to recall over the last 8 weeks all the contacts they have had with the healthcare service. This will be a modified version of the Client Service Receipt Inventory (CSRI).

We will also ask them to wear an actigraphy monitor on their wrist for one week and to complete a sleep diary at the same time. We will provide them with a prepaid envelope to send the materials back.

We will also record demographic variables including; age, sex, partner status, whether they share a bed, medications, employment status and date of stroke.

5.6. Subsequent Assessments

Participants randomised to the intervention group will receive access, via web link and activation code to the digital CBT-I programme “Sleepio”. This programme will require the participant to keep a daily sleep diary and engage in weekly sessions comprising weekly CBT-I content. Participants randomised to the control group will be given access to an online sleep diary to complete for one week. They will also receive a brochure with sleep hygiene information and then will be asked to complete the online sleep diary again 8 weeks later.

During the trial, participants will be asked to keep a record, in a specially designed log book, of their contacts with the healthcare service.

Upon completion of the programme, participants will once again be sent questionnaires to complete (PHQ-9, GAD-7, SIS-8, Stroke Efficacy questionnaire and EQ-5D-5L), in addition to the wrist worn actigraphy monitor and the sleep diary to use for one week.

At 8 weeks follow up, all assessments conducted as baseline will be repeated and the intervention group will complete a debriefing feedback questionnaire.

6. Feasibility and Adverse events

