1. SYNOPSIS

Long Study Title	An Investigation into the Efficacy of Online Cognitive Behaviour Therapy for Insomnia (“Sleepio”) for Stroke Survivors	
Short Study Title (to be used on participant-facing documents, if applicable)	Improving sleep in rehabilitation after stroke (INSPIRES)	
Nature of Study Participants	Stroke survivors	
Intended number of participants	86	
Design	Randomised controlled	
Location	In the participant's home / online	
	Objectives	Outcome Measures
Primary	The primary objective of this study is to assess whether self-reported sleep quality in stroke survivors is improved following online Cognitive Behavioural Therapy for Insomnia (“Sleepio” programme).	The primary outcome measures for this study will be the change in Sleep Condition Indicator score following completion of the programme.
Secondary	
The secondary objectives are to assess changes in measures of sleep quality and self-reported measures of quality of life and anxiety following the intervention and at 8 week follow up.
 
To assess the cost-effectiveness of online CBT-I in stroke survivors when compared to a brochure of sleep hygiene information.
	
Changes in sleep fragmentation and wake after sleep onset, assessed with actigraphy, sleep onset latency assessed through the sleep diaries, anxiety and depression using the PHQ9 and GAD7, quality of life using the Stroke impact scale-8 and Euroqol-5 Dimensions- 5 Levels (EQ-5D-5L)
 
Changes in healthcare costs during the 8-week follow up.

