3. STUDY DESIGN

The study will be a single-blinded randomised controlled trial involving the completion of a six-week digital CBT-I programme. Following written informed consent, participants will be posted baseline questionnaires to complete and an actigraphy monitor to record objective sleep measures for one week. After this, participants will be randomised to CBT-I or control using an online randomisation software (rando.la) with minimisation of between group differences based on age and baseline self-reported sleep quality (Sleep Condition Indicator (SCI) score). The control group will be given access to an online sleep diary to complete daily for one week. They will also be given a brochure containing sleep hygiene information. 8 weeks later they will be asked to complete the online sleep diary again for one week.

Participants allocated to Sleepio will complete daily online sleep diaries for the duration of the study and will receive weekly online CBT-I sessions as part of the programme. Both groups will complete their programmes at home.

Participants will be sent the questionnaires and actigraphy monitor again to be worn for another week immediately following completion of the programme (Sleepio) or following the 6-week sleep diary (control) and at 8 weeks follow up. At 8 weeks follow up, participants in the intervention group will also be sent a debriefing questionnaire to get feedback on the programme and the research study.

Participants allocated to the control group will be sent a web link and activation code for the Sleepio programme following completion of the 8 week follow up.

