8. STATISTICS AND ANALYSIS

8.1. Description of Statistical Methods

The efficacy of Sleepio will be assessed by comparing the SCI scores of the intervention and control groups from baseline to immediately post-intervention, following an intention to treat analysis approach. Changes in the primary outcome measure from baseline to post-intervention will be assessed with analysis of variance (ANOVA) (or linear mixed model or non-parametric equivalents if necessary) with inclusion of baseline score as a covariate.

Secondary outcomes will be assessed with ANOVA (or linear mixed model or non-parametric equivalents if necessary). EQ-5D-5L responses will be converted into utility values using population preferences (van Hout et al., 2012) and combined with survival information to calculate Quality Adjusted Life-Years (QALYs). All resource use will be valued using 2018/19 unit costs obtained from healthcare compendiums, (Curtis and Burns 2018) NHS reference costs, (<https://improvement.nhs.uk/resources/reference-costs/>) and British National Formulary (<https://www.bnf.org/>). Costs of CBT-I will be obtained from the trial.

An incremental analysis will be performed, assessing the differences in costs between the two interventions and dividing by the difference in QALYs gained in order to generate an incremental cost-effectiveness ratio (ICER). ICERs will be estimated using an NHS perspective. The 10 000 bootstrapped pairs of incremental costs and incremental QALYs will be plotted on cost-effectiveness planes to display the uncertainty in the estimated ICER. Cost-effectiveness acceptability curves (CEACs) will be derived to display the probability of the CBT treatment being cost-effective, as the ceiling ratio for the maximum acceptable cost-effectiveness ratio varies from £0 to £85 000 per QALY gained.

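### The itemised post-intervention questionnaire list in section 5.6 leaves out the Sleep Condition Indicator, the primary outcome at its primary time point

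*Combined protocol and SAP*

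**What the plan says.** The primary outcome is defined consistently in two places. Section 1 (Synopsis) states: "The primary outcome measures for this study will be the change in Sleep Condition Indicator score following completion of the programme". Section 8.1 sets the primary analysis as "comparing the SCI scores of the intervention and control groups from baseline to immediately post-intervention", with the baseline score as a covariate.

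For baseline, section 5.5 says "the participant will be sent the GAD-7, PHQ-9, SCI, Stroke Impact Scale-8, Stroke Efficacy questionnaire and EQ-5D-5L to complete". A modified Client Service Receipt Inventory (CSRI), actigraphy and a sleep diary are described separately.

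For the post-intervention assessment, section 3 says "Participants will be sent the questionnaires and actigraphy monitor again to be worn for another week immediately following completion of the programme" (or, for controls, after their diary period). It does not name the instruments. Section 5.6 does name them: "participants will once again be sent questionnaires to complete (PHQ-9, GAD-7, SIS-8, Stroke Efficacy questionnaire and EQ-5D-5L", and then "in addition to the wrist worn actigraphy monitor and the sleep diary to use for one week". The SCI appears in neither part.

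For the last time point, section 5.6 says "At 8 weeks follow up, all assessments conducted as baseline will be repeated", which brings the SCI back.

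**The concern.** The section that tells staff what to send at the primary time point does not include the instrument on which the trial's main conclusion rests. Questionnaires are posted to participants' homes, so a pack made up from the section 5.6 list would go out without the SCI, and nothing later in the procedures would catch the gap.

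The loss could not be made good. A self-reported score for a missed time point cannot be collected afterwards. The SCI at 8 weeks follow-up measures persistence of effect, whereas section 8.1 places the primary comparison immediately after the intervention. If section 5.6 were followed to the letter, the primary analysis could not be run.

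**Working it through.** The plan gives no figure on this point, so the check is a comparison of the assessment lists by time point.

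| Questionnaire | Baseline (5.5) | Post-intervention (5.6) | 8 weeks follow-up (5.6) |
|---|---|---|---|
| GAD-7 | named | named | all baseline assessments |
| PHQ-9 | named | named | all baseline assessments |
| Stroke Impact Scale-8 | named | named | all baseline assessments |
| Stroke Efficacy | named | named | all baseline assessments |
| EQ-5D-5L | named | named | all baseline assessments |
| SCI | named | **absent** | all baseline assessments |

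1. **Count.** There are six questionnaires in the baseline sentence and five in the post-intervention list: 6 − 5 = 1 missing, the SCI.
2. **Is the list meant as examples?** Nothing marks it as partial. It names the instruments one by one and then adds actigraphy and the diary. The sentence on the 8-week assessment, in the same section, calls for the full baseline set. Read literally, section 5.6 therefore prescribes a shorter set after the intervention and the complete set only at follow-up.
3. **Is the SCI collected another way?** No section describes post-intervention SCI collection by telephone, through the online diary or through the Sleepio platform. The platform could not serve controls in any case, since they receive access only after the 8-week follow-up (sections 3 and 5.4).
4. **What do the other sections require?** Sections 1 and 8.1 require a post-intervention SCI. Section 3 implies it, because its reference to the questionnaires being sent again points back to the baseline set.
5. **The CSRI** is also absent from the post-intervention list. It is left out of this point because section 5.6 provides a log book of healthcare contacts during the trial.
6. **Effect on the sample size.** None. As a background check on section 8.2, a two-sample t-test with d = 0.7, two-sided alpha 0.05 and 80% power needs 33.02 per arm. Rounded up, that is 34 per arm and 2 × 34 = 68 in total, the plan's own figure. It does not depend on the list in section 5.6, provided the SCI is collected.

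**The case against.** The strongest reply is that this is an incomplete list and not a conflict over the endpoint. No section says that the SCI will not be collected after the intervention, and sections 1 and 8.1 agree on the outcome and its timing. The wording of sections 3 and 5.6 points back to the baseline questionnaires, which include the SCI. Only one primary endpoint is defined, so a careful reader would not be misled. The harm arises only if packs were built from one parenthesis and the rest of the protocol was ignored, and the documents do not rank section 5.6 above the others.

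Much of this stands. The intent can be recovered, the omission is probably a slip, and the harm is conditional. It does not remove the conflict: followed as written, section 5.6 would not produce the data that section 8.1 analyses, and no rule says which section prevails. Clear intent shows how to correct the text; it does not make the correction unnecessary.

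A second reply also stands, as a separate matter. Section 5.6 ties the post-intervention pack to completing the programme and gives no time for controls. Section 3 ties the control assessment to a 6-week diary, although sections 3 and 5.6 elsewhere describe a one-week control diary repeated 8 weeks later. Adding the SCI to the list does not settle that.

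**Conclusion.** The point holds. One of the six questionnaires named at baseline is missing from the only itemised post-intervention list, and it is the primary outcome at the primary time point. The conclusion rests on the text alone and needs no numerical assumption.

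The size of the problem depends on practice. If the SCI is sent as sections 1 and 8.1 require, nothing quantitative changes. If packs follow section 5.6 literally, no post-intervention SCI exists in either arm and the primary analysis is lost. The documents do not show which applies. Because the possible loss is total and irrecoverable while the correction is trivial, it must be made.

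**What to change.** In section 5.6, amend the post-intervention list to read: SCI, PHQ-9, GAD-7, SIS-8, Stroke Efficacy questionnaire and EQ-5D-5L. State that it applies to both arms and that the SCI at this time point is the primary endpoint assessment. The list then agrees with sections 1, 3 and 8.1 on content. Check that the posted post-intervention packs contain the SCI.

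The cost is a one-word correction to the list with a short label, and at most one more short questionnaire in a pack that is already being posted. No sample size, alpha or power figure changes. The timing of the control arm's post-intervention assessment should be reconciled between sections 3 and 5.6 as a separate correction.

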6.1. Feasibility of recruitment and adherence

We will record the number of people who express an interest in participating, the number who consent and the number who complete the study as an estimate of feasibility of recruitment to the study and completion of the CBT-I programme for this population.

Where known, we will record any reason for declining to take part or withdrawal from the study.

We will also send a debriefing questionnaire to participants at the end of the study to ask for their opinions of the study and the sleep improvement programme, and whether they had any CBT-I from other sources during the course of the study.

6.2. Adverse events

We will record any adverse effects that we are notified of, regardless of group allocation.

7. Definition of End of Study

The end of study is the date of the last follow-up response of the last participant.

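### Adverse effects are recorded only on notification and no follow-up questionnaire is stated to ask about them, so harms would probably be under-recorded in both arms, and counts could differ by arm for reasons other than treatment

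*Combined protocol and SAP*

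**What the plan says.** Section 6.2 deals with recording of harms in a single sentence: "We will record any adverse effects that we are notified of, regardless of group allocation". The document does not define an adverse effect, set a time at which participants are asked about one, grade seriousness or say how events will be tabulated.

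Contact during the trial is described as follows.

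- **Sleepio arm (Section 3):** "Participants allocated to Sleepio will complete daily online sleep diaries for the duration of the study and will receive weekly online CBT-I sessions".
- **Control arm (Section 5.6):** "Participants randomised to the control group will be given access to an online sleep diary to complete for one week". Controls also receive a sleep hygiene brochure and repeat the diary 8 weeks later.
- **Both arms, post-intervention (Section 5.6):** "Upon completion of the programme, participants will once again be sent questionnaires to complete". The list is PHQ-9, GAD-7, SIS-8, the stroke efficacy questionnaire and EQ-5D-5L, with actigraphy and a diary.
- **Both arms, 8 weeks (Sections 5.5 and 5.6):** the baseline set is repeated, including the modified CSRI recall of healthcare contacts.
- **Throughout, with no restriction by arm (Section 5.6):** "participants will be asked to keep a record, in a specially designed log book, of their contacts with the healthcare service".
- **Debriefing form:** Section 5.6 says "the intervention group will complete a debriefing feedback questionnaire", and Section 3 agrees. Section 6.1 says "We will also send a debriefing questionnaire to participants at the end of the study", without naming an arm.

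**The concern.** A rule that waits for notification captures what happens to be reported. Nobody meets the participant at a scheduled visit in this trial, so an event that is not written down or telephoned in has little chance of being seen. That makes the harms record incomplete whatever the arm.

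The second worry is comparability. Applying the same recording rule to both arms does not give an event the same chance of reaching the team in both. If one arm has more occasions to mention a problem, its recorded count may be higher for that reason alone. A reader of the trial report who sees events listed by arm could not tell a treatment effect from a reporting effect. Events not asked about during follow-up cannot be fully recovered afterwards.

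**Working it through.** The plan states no adverse-event rate, reporting rate or safety sample size, so there is no figure to reproduce. The check is mainly a reading of the text, followed by an illustration on assumed values.

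**Step 1. Does any listed instrument ask about adverse effects?**

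- Post-intervention and 8-week questionnaires: none is stated to do so.
- Log book and CSRI: they record healthcare contacts. The only use the plan describes for resource-use data is costing (Section 8.1). An event that led to no contact would not appear.
- PHQ-9, GAD-7, SIS-8 and EQ-5D-5L: these would show worsening mood, anxiety, function or quality of life at two time points, but not discrete events.
- Debriefing form: Sections 3 and 6.1 describe feedback on the programme and the study, and any CBT-I from elsewhere. Adverse effects are not listed.
- Withdrawal reasons: recorded only where known (Section 6.1).

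Capture outside Section 6.2 is therefore partial.

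**Step 2. Does contact differ by arm?** In programme use, yes: daily diaries and weekly sessions against a brochure and separate diary weeks. (Section 3 also refers to a 6-week control diary, which does not fit the one-week periods given elsewhere.) In direct contact with the team, the only documented difference is the debriefing form, and that depends on whether Sections 3 and 5.6 or Section 6.1 is followed.

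**Step 3. Illustration.**

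Inputs from Section 8.2: recruitment target 86 and 1:1 allocation, so 86 / 2 = 43 per arm.

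Assumed, not in the documents: the same true risk r in both arms, and reporting probabilities p_S (Sleepio) and p_C (control).

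- Expected recorded participants per arm = 43 × r × p
- Apparent risk ratio = (43 × r × p_S) / (43 × r × p_C) = p_S / p_C

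With r = 20%, 43 × 0.2 = 8.6 participants per arm truly have an event, 17.2 in all.

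| p_S v p_C | Recorded, Sleepio v control | Apparent risk ratio | Missed, out of 17.2 |
|---|---|---|---|
| 90% v 90% | 7.7 v 7.7 | 1.00 | 1.7 |
| 90% v 70% | 7.7 v 6.0 | 1.29 | 3.4 |
| 90% v 50% | 7.7 v 4.3 | 1.80 | 5.2 |
| 70% v 30% | 6.0 v 2.6 | 2.33 | 8.6 |
| 50% v 90% | 4.3 v 7.7 | 0.56 | 5.2 |

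Missed = 8.6 × (1 − p_S) + 8.6 × (1 − p_C). For 90% v 50% this is 0.86 + 4.30 = 5.2.

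The risk ratio does not depend on r, so it is the same at a true risk of 10% or 30% (4.3 or 12.9 true cases per arm). It only restates the assumed reporting ratio. The last row reverses the direction, because the documents do not settle it. The table shows how the mechanism works and is no estimate for this trial.

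**The case against.** The strongest case against the point has four parts.

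1. **More programme use is not more notification.** Sleepio is an online programme reached by web link and activation code. Nothing says that the team reads the diaries or sessions, or that they serve as a reporting route. This stands. A reader might infer that the counts are bound to be non-comparable, or bound to be inflated in the Sleepio arm. The documents do not support that: they show that counts could differ, not that they would, nor which way.
2. **Shared contact is substantial.** Both arms get the same postal packs at the same two points, the service-use recall at 8 weeks, and the log book. Section 8.1 also uses survival information for QALYs. Notice need not come from the participant, since Section 6.2 names no source and Section 4.2 anticipates carer help. This stands and narrows the between-arm gap. It does not supply a question about adverse effects.
3. **The programme is not new to stroke survivors.** A reader might take Section 2 to mean that it is untried in this population, so that harms are wholly unknown. In that passage it is efficacy that is said to be untested, and the next sentence reports a completed feasibility study in stroke survivors; Section 8.2 draws on an open-label feasibility study. Neither passage reports safety results, but lack of prior use cannot carry the argument.
4. **No planned analysis depends on the counts.** Section 1 has no safety objective and Section 8.1 plans no between-arm comparison of harms. This stands and limits the severity.

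What remains after these concessions is the under-recording. It does not rely on any difference between arms.

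**Conclusion.** The concern holds in a limited form. As written, harms capture is incomplete by design in both arms, because Section 6.2 is passive and no listed questionnaire is stated to ask. This rests on reading the instrument lists in Sections 5.5 and 5.6 as complete. That it would lead to under-recording is a judgement, a probable one given remote and postal delivery.

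A difference between arms for reasons other than treatment is possible. Its size and direction cannot be computed from the documents. The ratios above, from 0.56 to 2.33 and exactly 1.00 with equal reporting, follow entirely from assumed reporting rates and should be cited only on that footing.

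The SCI analysis, the secondary outcomes and the cost-effectiveness analysis are unaffected. The change is worth making because it is cheap and the information is hard to recover later, not because the main result is at risk.

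**What to change.** Change Section 6.2 so that one identical adverse-effect question (what happened, when, and whether it was serious) goes into the post-intervention and 8-week packs of both arms. Keep recording spontaneous reports from any source. Report counts by arm, stating for each event whether it was solicited or spontaneous.

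Reconcile Sections 3 and 5.6 with Section 6.1 on who receives the debriefing form, so that any difference in contact between arms is known and can be described.

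The cost is one question in two mailings that both arms already receive. It needs no extra visit and leaves treatment, sample size and the efficacy analyses alone. The downside is a few more events to log.
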